4.2 Rationale for the Proposed Study

CVN766 is a highly selective orexin-1 receptor (Ox1R) antagonist and may have utility as a treatment for psychiatric disorders including schizophrenia, panic disorder and anxiety, and addiction. Its safety and PK profile have been preliminarily established in nonclinical toxicology studies. The present study will be the first conducted in humans with CVN766 and will examine the compound's safety, tolerability, and PK in healthy subjects.

Nonclinical pharmacology, toxicity, and pharmacokinetic (PK) studies support the proposed escalating single- and multiple-dose study of CVN766 in healthy subjects with a starting dose of 5 mg. **Section 6.2** outlines the justification for the planned dose ranges.

5.0 STUDY OBJECTIVES AND ENDPOINTS

5.1 Objectives

5.1.1 Primary Objective

- To characterize the safety and tolerability profile of escalating dose levels of CVN766 suspension when administered as a single oral dose or daily oral doses for 7 days in healthy subjects

5.1.2 Secondary Objectives

- To characterize the single-dose PK profile of CVN766 in plasma, and CSF
- To characterize the multiple-dose PK profile of CVN766 in plasma, and CSF
- To assess the effect of food on the bioavailability of CVN766 in the current formulation

5.1.3 Exploratory Objectives

- To explore possible drug metabolic enzyme and transporter polymorphisms that may contribute to variability in CVN766 PK, pharmacodynamics, or safety

5.2 Endpoints

5.2.1 Primary Endpoints

- Percentage of subjects who experience at least one treatment-emergent adverse event (TEAE)
- Percentage of subjects with abnormal and clinically significant (CS) safety laboratory test results at least once post-dose
- Percentage of subjects with abnormal and CS electrocardiogram (ECG) test results at least once post-dose
- Percentage of subjects with abnormal and CS vital sign measurements at least once post-dose

5.2.2 Secondary Endpoints

- Single-dose plasma PK parameters of CVN766, including time to maximum plasma concentration (T_{max}), area under the plasma concentration-time curve from time 0 to 24 (AUC_{24}) and time 0 to infinity (AUC_{∞}), and terminal elimination half-life ($t_{1/2z}$)

- Multiple-dose plasma PK parameters of CVN766 including C_{max} , AUC from time 0 to the end of the dosing interval, $t_{1/2z}$, accumulation ratio, time to steady-state, steady-state C_{max} , and steady-state C_{min}
- Single-dose and multiple-dose CSF concentrations and CSF: plasma ratios of CVN766

5.2.3 Additional Endpoints

- Change from baseline in safety laboratory and ECG test results and vital signs
- Additional plasma PK parameters of CVN766, i.e., CL/F and V_z/F

[figure not shown]
- Characterization of metabolic enzyme and transporter polymorphisms

6.0 STUDY DESIGN AND DESCRIPTION

6.1 Study Design

This is a Phase 1 ascending study in healthy subjects. Figure 1 provides a schematic illustration.

Figure 1 Study Schema

6.1.1 Part 1: Single-Dose Regimen and Fasted-Fed Crossover

Approximately 40 subjects will be enrolled in 1 of the 5 single-dose cohorts (designated as S1 through S5, respectively) in an ascending fashion. An optional Cohort 3a may be added in parallel to SC3 for additional safety and tolerability evaluation. Cohort S3a dose level will be consistent with Cohort S3 (45 mg planned) in a fasted condition only and without lumbar puncture, aligned with the Schedule of Procedures (**Appendix A**) and other SAD cohorts. Dose escalation will only occur after a fully blinded review of all available safety, tolerability, clinical laboratory results (minimally including samples collected from subjects through 72-hours post-dose), and available PK data, including at least a 72-hour follow-up from a minimum of 5 subjects of the most recent cohort.

The planned dose levels are provided in **Table 5**. Each cohort will consist of 8 subjects randomized to CVN766 or placebo, whereby 6 subjects will receive a single dose of CVN766 and 2 subjects will receive a matching placebo under overnight fasted conditions.

Sentinel dosing (1 subject to receive CVN766 and 1 subject to receive placebo) will be used in each cohort to ensure adequate safety and tolerability evaluation prior to administering CVN766 to the remainder of the subjects within the cohort. After a blinded review of 24-hour post-dose safety and tolerability data, the remaining 6 subjects of each cohort may be dosed, provided that the adverse event (AE) profile of CVN766 in the first 2 subjects is considered acceptable.

Subjects for all cohorts (including optional Cohort S3a) will be admitted to the study unit 1 day prior to dosing and remain in the unit for safety and PK assessments at least 72 hours after dosing. On Day 1, subjects will undergo safety monitoring (including labs, physical exam, neurological exam, cardia telemetry at 12-hours pre-dose), and PK sampling from blood plasma through 72 hours post-dose. In addition, for Cohort S3 (fasted) only, from CSF via lumbar puncture at 3 hours post-dose. For subjects participating in the SAD cohorts, the total confinement period will be 4 nights unless extended for management of AEs at the discretion of the Investigator. Follow-up assessments will occur on approximately Days 8 and 14.

To assess the effect of food on bioavailability of CVN766 in suspension formulation, single-dose administration will be repeated in a single cohort after ingestion of a standardized high-fat high-calorie meal according to FDA Guidance for Industry (Food-effect bioavailability and fed bioequivalence studies, Dec 2002). Once the safety of the S3 Cohort dose level has been assessed, the S3 Cohort subjects will return to the clinic (no sooner than 14 days after their prior dose, or at least 4 half-lives has lapsed based on preliminary PK data, whichever is longer) and will receive the same dose as before, administered after ingesting a standardized breakfast. Subjects will finish at least approximately 85% of their breakfast within 30 minutes and will receive an investigational product 30 minutes (± 5 minutes) after beginning the meal. Sentinel dosing will not be required for subjects returning to the clinic for the fed regimen. If the CVN766 PK parameters in the fasted S3 Cohort reveal poor absorption with inconclusive results, the fed cohort will be deferred until a higher dose level.

An outline of the single-dose study visit schedule is included in **Table 1**. A Schedule of Study Procedures is listed in **Appendix A**.

Table 1 Single-Dose Visit Schedule

Screening ^a	Inpatient Check-in	Dosing, PK, CSF & Safety Assessments ^b	Inpatient PK & Safety Assessments	Inpatient Discharge ^c	Follow-Up Outpatient Visit	Follow-Up Call ^d
Day -28 to -2	Day -1	Day 1	Day 2-4	Day 4	Day 8 ±1 day	Day 14 ±2 days

- (a) Screening will occur at study entry. Subjects returning for the “Fed” repetition of the single-dose regimen will not undergo Screening assessments except as required at Day -1.
- (b) CSF collection will apply only to Cohort S3 (fasted).
- (c) Discharge from the clinic may be delayed if necessary to continue monitoring for resolution of AEs.
- (d) The final follow-up assessment will occur by telephone unless abnormal CS findings are observed upon discharge. In these cases, subjects must return to the clinic for re-evaluation.

6.1.2 Part 2: Multiple-Dose Regimen

For the multiple-dose regimen, approximately 24 subjects will be enrolled in 1 of the 3 multiple-dose cohorts (designated as M1 through M3, respectively) in an ascending fashion. Dosing will be administered in the fasting state; this can be changed by the SRG if exposure is found to be higher in the fed state. The dose levels planned to be studied in the multiple-dose regimen (M1 through M3) are provided in **Table 5**. Each multiple-dose cohort will consist of 8 subjects randomized to CVN766 or placebo, whereby 6 subjects will receive a daily dose of CVN766, and 2 subjects will receive matching placebo for 7 days. However, the duration may be increased to ≤14 days at the discretion of the safety review group (SRG) if preliminary PK data suggest steady-state will not be achieved within 6 days of daily dosing. Unlike the single-dose regimen, sentinel dosing within cohorts is not required in the multiple-dose regimen.

Subjects for all multiple-dose cohorts will be admitted to the study unit 1 day prior to dosing and remain in the unit for the duration of the dosing period and for at least 48 hours after the last dose for safety and PK assessments before discharge. On treatment Days 1 and 7, subjects will undergo safety monitoring and PK sampling from blood plasma through 48 hours post-dose and, in Cohort M1 only, from urine through 24 hours post-dose. In Cohorts M1 and M2, on treatment Day 7 (or last day of dosing, if extended beyond Day 7), subjects will undergo additional PK sampling from CSF via lumbar puncture at 3 hours post-dose. If the SRG determines additional PK sampling from CSF via lumbar puncture is not necessary for Cohort M2, the lumbar puncture may be omitted. Likewise, if needed to resolve questions arising from prior Cohorts’ data, subjects in Cohort M3 also may, at SRG discretion, undergo PK sampling from CSF via lumbar puncture, the choice of day (e.g., Day 1 or Day 7) and sampling time to be decided by SRG. Subjects in MAD cohorts may be asked to return to the clinic for an additional plasma PK sample 3 days after the last dose (e.g., Day 10) depending on emerging PK data, i.e., $t_{1/2}$. The total confinement period will be 9 nights unless extended for additional dosing days or management of AEs. Follow-up assessments will occur approximately 7 and 14 days after the final dose. A summary of multiple-dose study visits is included in **Appendix A**.

Table 2 Multiple Dose Visit Schedule

Screening	Inpatient Check-in	Dosing, PK, CSF, & Safety Assessments ^{a,f}	PK / Safety Assessments & inpatient discharge ^b	Follow-Up Outpatient Visits ^c	Follow-Up Call ^d
Day -28 to -2	Day -1	Days 1-7 ^e	1 and 2 days after last dose (e.g. Days 8-9)	3 days ±0 after last dose (e.g. Day 10) & 7 days ± 1 after last dose (e.g. Day 14)	14 days ±2 after last dose (e.g. Day 21)

- (a) CSF sampling is planned on Day 7 in Cohorts M1 and M2 (CSF sampling for Cohort M2 may be omitted at the discretion of the SRG). Cohort M3 also may, at SRG discretion, undergo PK sampling from CSF, the choice of day and sampling time to be decided by SRG.
- (b) Discharge from the clinic is planned for Day 9 but may be delayed for additional dosing days or if necessary, to continue monitoring for resolution of AEs.
- (c) If emerging PK data indicate the CVN766 $t_{1/2}$ is 15 hours (or less), the visit 3 days after the last dose (e.g., Day 10) may be omitted at Investigator’s discretion.
- (d) The Follow-up Visit will occur by telephone unless abnormal CS findings are observed upon discharge. In these cases, subjects must return to the clinic for re-evaluation.
- (e) Dosing duration may be increased to ≤14 days at the discretion of the SRG based on preliminary PK and projected time to steady-state.
- (f) Urine sampling will occur on Day1 and Day 7 in Cohort M1.

6.1.3 Dose Escalation

The SRG will comprise the Investigator, Medical Monitor, Cerevance Responsible Medical Officer and may include other Cerevance representatives. A pharmacokineticist and other subject matter experts may participate as needed. The SRG will be responsible for the ongoing review of safety, tolerability, clinical laboratory results, and available PK data and deciding to:

- Escalate to the next planned cohort or alternative dose levels (e.g., lower, intermediate, or higher) in single-dose cohorts (based on a review of available data, including at least 72 hours post-dose safety data and clinical laboratory results from a minimum of 6 evaluable subjects in the current cohort),
- Escalate to the next planned cohort or alternative dose levels (e.g., lower, intermediate, or higher) in multiple-dose cohorts (based on a review of available data, including at least 48 hours post 7th dose safety data from a minimum of 6 evaluable subjects in the current cohort),
- Add additional dose cohort(s) in either the single- or multiple-dose studies,
- Increase the duration of dosing in the multiple-dose cohorts from 7 days to ≤14 days

If 2 or more subjects in a single cohort experience the same type of serious or medically adverse event, further dosing will be withheld until the SRG investigates the events. Based on this assessment, the SRG will determine if the study should be terminated or continued and whether modification of planned dose levels and/or implementation of additional safety monitoring is indicated.

For each cohort (including sentinel subjects, where applicable), the SRG will carefully review the available blinded safety, tolerability, clinical laboratory results, and available PK data to determine whether dosing should stop or continue (and, if continued, at what dose, including whether to repeat the previous dose), whether additional sequential dosing should be implemented in future cohorts or whether the blind should be broken to identify whether the subjects received CVN766 or placebo. However, precautions must be taken not to unblind the study staff, including the Investigator.

If all doses are tolerated, then additional cohorts with higher doses may be considered. The actual choice of the subsequent dose level will occur after the full review of the available blinded safety, tolerability, clinical laboratory results, and available PK data in the preceding cohort. The subsequent dose level may be higher, lower, or remain the same as the prior dose level. If necessary, additional cohort(s) may be added to fully characterize the safety and tolerability of CVN766.

Initiation of the multiple-dose regimen will only occur after a full blinded review of all available safety, tolerability, and clinical laboratory results for the fasting drug administration to single-dose Cohort S3 (minimally including samples collected through Day 4) and available PK data. For each multiple-dose cohort after the first, the actual choice of dose level may be modified by the SRG after a review of the available blinded safety, tolerability, and clinical laboratory results, and available PK data in the preceding multiple-dose and next-higher-dosage single-dose cohorts (i.e., multiple-dose Cohort M2 will not initiate until the data review for multiple-dose Cohort M1 and single-dose Cohort S4 is complete). Each subsequent dose level may be higher, lower, or remain the same as the preceding dose level.

Additional multiple-dose cohort(s) may be added if deemed necessary by the SRG to fully characterize the safety and tolerability of CVN766. Such additional cohorts will follow the same schedule of events as for prior multiple-dose cohorts. Additional/Alternative PK timepoints may be implemented if the SRG determines this is necessary to fully characterize the PK profile of CVN766.

All AEs reported during the Treatment Period, both within and across cohorts, up to the time of discharge, will be evaluated to assess the need for the subject and/or study termination in accordance with the prespecified criteria for discontinuation/termination (**Section 6.3.1**).

Additionally, the SRG may decide not to escalate the dose for a particular cohort but rather administer the same or a lower dose level to the next cohort. Additional/ Alternative PK timepoints may be implemented if the SRG determines this is necessary to fully characterize the PK profile of CVN766.

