
Study Design:
 
This is a Phase 1, randomized, double-blind, placebo-controlled, single- and multiple-dose ascending study in healthy subjects with concurrent PK sampling from blood plasma, urine, and cerebrospinal fluid. The overall study design is outlined below:
 
Part 1: Single-Dose Regimen and Fasted-Fed Crossover
 
For the single-dose regimen, approximately 40 healthy male or female subjects will be enrolled in 1 of 5 single-dose cohorts (designated as S1 through S5, respectively) in an ascending fashion. An optional 8 subject (Cohort S3a) may be added in parallel with Cohort S3. Cohort S3a dose level will be consistent with Cohort S3 (45 mg planned) in a fasted condition only and without lumbar puncture, aligned with the Schedule of Procedures (Appendix A) and other SAD Cohorts. Each cohort will consist of 8 subjects randomized to CVN766 or placebo. In each cohort, 6 subjects will receive a single oral dose of CVN766 suspension, and 2 subjects will receive a matching placebo suspension under overnight fasted conditions. Subjects will remain fasted for 4 hours post-dose. Consumption of water is permitted as desired except for 1 hour before and after administration of Study Drug. Sentinel dosing (1 subject to receive CVN766 and 1 subject to receive placebo) will be used in each cohort to ensure adequate safety and tolerability evaluation prior to administering CVN766 or placebo to the remainder of the subjects within the cohort. After blinded review by the Investigator of 24-hour post-dose adverse event listings (as applicable) from the sentinel group, the Investigator will advise the sponsor on the acceptability of enrolling the remaining 6 subjects in each cohort. In the event that a safety signal emerges in the sentinel group, a Safety Review Group (SRG) meeting may be required as requested by Investigator or Sponsor. To accommodate the lumbar puncture in the S3 fasted cohort, the remaining 6 subjects' dosing may be staggered every two days after the sentinel group. The planned dose levels will be 5, 15, 45, 125, and 250 mg CVN766. The SRG will review all available blinded safety, tolerability, clinical laboratory results (minimally including samples collected from subjects through 72-hours post-dose), and available pharmacokinetic (PK) data prior to all dose escalations and after the completion of all subjects in a cohort. If Cohort S3a (optional cohort) is enrolled and completed prior to Cohort 3, the SRG may determine dose escalation to Cohort S4 after evaluating data from Cohort 3a alone. Each following dose level may be higher, lower, or remain the same as the preceding cohort, dependent on the recommendation of the SRG.
 
Additional cohort(s) may be added if deemed necessary by the SRG to fully characterize the safety and tolerability
		

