
clinical laboratory results from a minimum of 5 subjects in the current cohort),
 
 2. Escalate to the next planned cohort or alternative dose levels (e.g., lower, intermediate, or higher) in multiple-dose cohorts (based on a review of available data, including at least 48 hours post 7th dose safety data from a minimum of 5 subjects in the current cohort), 3. Add additional dose cohort(s) in either the single- or multiple-dose studies, 4. Increase the duration of dosing in the multiple-dose cohorts from 7 days to ≤ 14 days, 
In addition, if 2 or more subjects in a single cohort experience the same type of serious or medically significant event, further dosing will be withheld until the SRG investigates the events. Based on this assessment, the SRG will determine if the study should be terminated or continued and whether modification of planned dose levels and/or implementation of additional safety monitoring is indicated.
	

Primary Objective:
 
To characterize the safety and tolerability profile of escalating dose levels of CVN766 suspension when administered as a single oral dose or daily oral doses for 7 days in healthy subjects and determine the recommended phase 2 dose (RP2D).
	

Secondary Objectives:
 
 • To characterize the single-dose PK profile of CVN766 in plasma and CSF • To characterize the multiple-dose PK profile of CVN766 in plasma and CSF • To assess the effect of food on the bioavailability of CVN766 	

Exploratory Objectives:
 
 • To explore possible drug metabolic enzyme and transporter polymorphisms that may contribute to variability in CVN766 PK, pharmacodynamics, or safety 	

Subject Population: Healthy male and female subjects 18 to 55 years old
	

Number of Subjects:
 
Each dose cohort: 8 subjects (6 active:2 placebo) Estimated total: 64 subjects (5 single-dose cohorts, 3 multiple-dose cohorts)
	
Number of Sites:
 
2 (Australia)

Dose Level(s):
 
Planned single-dose levels are placebo, 5 mg, 15 mg, 45 mg, 125 mg, and 250 mg CVN766. Planned multiple dose levels are placebo, 45 mg, 125 mg, and 250 mg CVN766.
	
Route of Administration:
 
Oral

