6.2 Justification for Study Design, Dose, and Endpoints

The study is double-blind and placebo-controlled to avoid subjective bias in assessing the safety and tolerability of CVN766. Dose escalation will be predicated on a review of available blinded safety, tolerability, and PK data from a minimum of evaluable 6 subjects from the prior Cohort.

The sponsor has selected the starting dose level considering the FDA Guidance for Industry (Estimating the Maximum Safe Starting Dose in Initial Clinical Trials for Therapeutics in Adult Healthy Volunteers, 06 July 2005) and providing additional safety factors to the initial calculations based on the principles outlined in the guidance. The toxicity profile of CVN766 after oral dosing was examined in repeat dosing studies in rats and dogs. Scaling based on body surface area was conducted by multiplying the NOAELs for the most sensitive animal species by the appropriate conversion factors. Based on these calculations and applying a 10-fold safety margin below the NOAEL human-equivalent dose (HED), the maximum recommended starting dose (MRSD) for this first-in-human study is 167 mg for a 60 kg subject. The selected starting dose level is 5 mg.

The study's multiple-ascending dose (MAD) portion seeks to prepare for subsequent repeat dosing studies in subjects. Each MAD dose level will have been studied or exceeded in the SAD portion of the study before its use in a MAD cohort.

Nonclinical toxicity study data provide a basis for calculating the maximum exposure level that can be presumed safe. Escalating to the HED of the NOAEL in the most sensitive animal species, the maximum dose for clinical use is 1670 mg/day.

The projected $t_{1/2z}$ in animal species ranged up to 6.5 hours, so sample collection through Inpatient Discharge 72 hours post-dose is expected to correspond to more than 5 half-lives and is anticipated to be adequate to document elimination of CVN766. The study design allows for collecting additional PK samples at later timepoints if preliminary emerging PK results are indicated.

AEs, physical exams, vital signs, ECG findings, and clinical laboratory results are used as safety assessments to determine dose tolerability and dose-limiting effects of CVN766. The plasma PK and CSF parameters and PK endpoints will help elucidate the pharmacology of CVN766.

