10.0 STUDY-SPECIFIC COMMITTEES

The Safety Review Group (SRG) will be comprised of the Investigator, Medical Monitor, Cerevance Medical Officer and may include other sponsor representatives. A pharmacokineticist and other subject matter experts may participate as needed. The responsibilities of the SRG are outlined in **Section 6.1.3**.

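### The minimum data for dose escalation is 5 subjects in two places and 6 evaluable subjects in two others, and only the synopsis lets Cohort S3a open multiple dosing

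*Protocol*

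**What the plan says.** The document contains two protocol versions. Everything cited here is from the later one, which introduces the optional Cohort S3a.

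**Minimum number of subjects**

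- Section 2.0, Safety Review Group, item 1 (single dose): 72-hour safety data and "clinical laboratory results from a minimum of 5 subjects in the current cohort".
- Section 2.0, Safety Review Group, item 2 (multiple dose): "48 hours post 7th dose safety data from a minimum of 5 subjects in the current cohort".
- Section 6.1.1 (single dose): escalation is conditional on a review "including at least a 72-hour follow-up from a minimum of 5 subjects of the most recent cohort".
- Section 6.1.3 (single dose): "clinical laboratory results from a minimum of 6 evaluable subjects in the current cohort".
- Section 6.1.3 (multiple dose): "48 hours post 7th dose safety data from a minimum of 6 evaluable subjects in the current cohort".
- Section 6.2 (dose escalation generally): data "from a minimum of evaluable 6 subjects from the prior Cohort".

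Section 10.0 adds: "The responsibilities of the SRG are outlined in" Section 6.1.3.

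**Role of Cohort S3a**

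- Section 2.0, Part 2: multiple dosing may start after review of fasted data from S3 or S3a.
- Section 6.1.3: multiple dosing may start only after review of fasted data from S3; S3a is not named.
- Section 2.0, Part 1: if S3a finishes before S3, the SRG may move to S4 on S3a data alone. The body sections do not repeat this.

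**The concern.** The escalation rule is the main conduct safeguard in an ascending-dose, first-in-human study, and here it has two written values. The values differ in kind as well as number. One text counts subjects and the other counts evaluable subjects, and the protocol does not define evaluable for this purpose. The SRG can meet one text and commit a deviation under the other. The same is true if it starts M1 on S3a data alone.

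A partly observed cohort is foreseeable. In the fasted S3 cohort the remaining subjects' "dosing may be staggered every two days after the sentinel group" to fit in the lumbar punctures. In any cohort a subject may withdraw after dosing, and Section 7.6 says such subjects are not replaced, although it also allows replacement at the sponsor's discretion. The multiple-dose cohorts have no required sentinel dosing, so the count carries more weight there.

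**Working it through.** The protocol has no figure to reproduce: the sample size is not power-based and neither minimum is justified numerically. The check has two parts.

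**1. The texts side by side**

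| Gate | Says 5 subjects | Says 6 evaluable |
|---|---|---|
| Single dose | Section 2.0 SRG item 1; Section 6.1.1 | Section 6.1.3; Section 6.2 |
| Multiple dose | Section 2.0 SRG item 2 | Section 6.1.3; Section 6.2 |

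| Gate | Synopsis | Section 6.1.3 |
|---|---|---|
| Opening M1 | S3 or S3a | S3 only |

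Preferring the body over the synopsis does not settle the single-dose gate, because Section 6.1.1 is body text, is worded as a condition and says 5. The pointer in Section 10.0 favours 6 but does not cancel Section 6.1.1. For opening M1, the two texts cannot both hold if only S3a has been reviewed.

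**2. What one subject is worth**

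Inputs: 8 subjects per cohort, 6 active (A) and 2 placebo (P) (Section 12.3); a sentinel pair of 1A and 1P in single-dose cohorts (Section 6.1.1); no required sentinels in multiple dosing (Section 6.1.2). The review is blinded, so the number treated among those counted is random. I assume those with data are a random subset, apart from the sentinels, who are always included.

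Single dose (sentinel pair, plus the rest drawn from 5A and 1P):

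- 5 reviewed: P(3A) = C(5,2)·C(1,1)/C(6,3) = 10/20 = 0.50; P(4A) = 10/20 = 0.50.
- 6 reviewed: P(4A) = C(5,3)·C(1,1)/C(6,4) = 10/15 = 0.67; P(5A) = 5/15 = 0.33.

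Multiple dose (drawn from 6A and 2P):

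- 5 reviewed: P(3A), P(4A), P(5A) = 20/56, 30/56, 6/56 = 0.36, 0.54, 0.11.
- 6 reviewed: P(4A), P(5A), P(6A) = 15/28, 12/28, 1/28 = 0.54, 0.43, 0.04.

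The guaranteed number on CVN766 is therefore 5 − 2 = 3 or 6 − 2 = 4.

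The chance of at least one event among k treated subjects is 1 − (1 − p)^k. The protocol gives no event risk, so p is assumed:

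| p | k = 3 | k = 4 |
|---|---|---|
| 0.10 | 0.271 | 0.344 |
| 0.20 | 0.488 | 0.590 |
| 0.30 | 0.657 | 0.760 |

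These compare the guaranteed minimums. Averaging over the allocation probabilities above gives smaller gaps:

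| p | Single dose, 5 vs 6 | Multiple dose, 5 vs 6 |
|---|---|---|
| 0.10 | 0.307 vs 0.366 | 0.325 vs 0.376 |
| 0.20 | 0.539 vs 0.618 | 0.563 vs 0.631 |
| 0.30 | 0.708 vs 0.784 | 0.731 vs 0.795 |

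For example, single dose at p = 0.10: 0.5 × 0.271 + 0.5 × 0.344 = 0.307 under the 5-subject rule, and (2/3) × 0.344 + (1/3) × 0.410 = 0.366 under the 6-subject rule, where 0.410 is the value for k = 5.

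**The case against.** The strongest reply is that both numbers are minimums, so waiting for 6 evaluable subjects satisfies every passage. Section 10.0 points to Section 6.1.3, Section 6.2 agrees with it, and for multiple dosing no body section says 5. This makes 6 the better-supported reading. It does not make 5 non-compliant for single dosing, and a safety gate should not depend on the SRG choosing the stricter of two rules.

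Second, the difference is one subject in eight and changes no endpoint, analysis set or estimate. Averaged over allocation, the detection gap is about 5 to 8 percentage points rather than the 7 to 10 between exactly 3 and exactly 4 treated. The withholding criteria in Section 6.3.1 generally need two similar cases, and they run across cohorts. Planned doses up to 125 mg are below the 167 mg maximum recommended starting dose, and 250 mg is about 15% (250/1670) of the 1670 mg/day stated maximum. All of this stands. It limits the likely harm, but it does not say which rule applies.

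Third, staggered dosing is stated only for fasted S3. Elsewhere a shortfall would come mainly from withdrawals or missing data, which are not random draws. This also stands, so the probabilities above are illustrative.

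Fourth, letting S3a open S4 does not contradict Section 6.1.3, whose single-dose rule refers to the current cohort without naming S3. That is correct. The true S3a conflict is confined to opening M1, and its consequence is modest because S3a has the same planned dose and fasting state as S3.

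**Conclusion.** The concern holds. The protocol sets the escalation minimum at 5 subjects in the synopsis and Section 6.1.1 and at 6 evaluable subjects in Sections 6.1.3 and 6.2. It also gives incompatible conditions for opening M1. These rules govern trial conduct, so a statistical analysis plan cannot repair them.

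The number rule matters by one guaranteed treated subject, 3 against 4. The detection figures rest on assumed event risks and random availability of data. They are floors, because the SRG reviews everything available, which may exceed the minimum. The M1 conflict does not change how many treated subjects are reviewed. The finding rests on the textual contradiction more than on these numbers, and it should be corrected because it is the escalation gate of a first-in-human trial.

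**What to change.** - Choose one minimum and one qualifier, and word them identically in Section 2.0 (SRG items 1 and 2), Section 6.1.1, Section 6.1.3 and Section 6.2. Six evaluable subjects is the safer of the two existing rules. If that term is kept, define who is evaluable for escalation.
- In Section 2.0, Part 1, the SRG reviews data before each escalation and also once all subjects in a cohort have completed. State whether completion of the cohort is a condition for escalating or a later second review.
- Make the S3/S3a conditions for opening M1 identical in Section 2.0 and Section 6.1.3. State in Section 6.1.3 whether S3a alone may open S4.

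The cost is protocol wording and, at most, waiting for one more subject's data before some escalations.
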